Study Protocol and Analysis Plan

Fixed Versus Weight-Based Enoxaparin Dosing in Thoracic Surgery Patients

NCT03251963

June 19, 2020

Study Design

Inclusion criteria were thoracic surgery patients, surgery under general anesthesia, and prophylactic enoxaparin initiation within 24 hours. Exclusion criteria were creatinine >1.6mg/dL, planned postoperative admission <3 days, epidural catheter, history of heparin induced thrombocytopenia, known bleeding issue, weight >150kg, or recent stroke or intracranial bleeding event. Most open thoracic surgery patients at both sites receive concomitant epidural anesthesia; this biased our sample toward the video-assisted thorascopic surgery (VATS) population. Patients provided written informed consent.

The study was designed prospectively as a pre/post trial to examine the impact of a change in practice (a switch from fixed dose to weight tiered enoxaparin). Cohort 1 accrued between September 21, 2017 and May 8, 2018, and all patients received fixed dose enoxaparin prophylaxis at 40mg once daily. Cohort 2 was planned as weight based at 0.5mg/kg, and recruitment began on May 9, 2018. Both sites encountered insurmountable issues with pharmacist dose rounding. Nine patients in the 0.5mg/kg group who received rounded doses were dropped. Cohort 2 was revised to weight-tiered, daily enoxaparin¹⁵. Patients <70kg received 30mg, patients 70kg to 89.9kg received 40mg, and patients \geq 90kg received 50mg. Cohort 2 accrued between August 9, 2018 and March 25, 2019. Figure 1 describes patient enrollment, exclusion, allocation, and followup.

We examined enoxaparin pharmacokinetics using steady state peak and trough aFXa levels, drawn at 4 and 12 hours after the third dose. Goal peak aFXa (0.3-0.5 IU/mL) was chosen to maximize VTE risk reduction while minimizing bleeding^{12,19}. All patients with identified out-of-range levels received dose adjustment and repeat aFXa levels per Figure 2. The algorithm targeted peak aFXa levels because low peak aFXa has been associated with symptomatic 90-day VTE⁹, because aFXa-driven dose adjustment is

impactful ⁸, and because a recent review showed that ~80% of studies targeted peak aFXa ^{19,20}. Dose adjustment was performed until an in-range peak level was achieved, or until time of discharge.

Patients received enoxaparin prophylaxis for the duration of inpatient stay. Post-discharge enoxaparin prophylaxis was not routinely provided; when given, patients were discharged on a pharmacokinetically optimized dose.

Study Outcomes

The primary effectiveness outcome was adequate peak aFXa (≥ 0.3 IU/mL), chosen because patients receiving enoxaparin 40mg once daily with initial peak aFXa < 0.3 IU/mL are at elevated risk for 90-day symptomatic VTE ⁹. The primary safety outcome was avoidance of over-anticoagulation (peak aFXa ≥ 0.5 IU/mL), which could increase risk for bleeding.

Secondary outcomes included 1) achievement of adequate trough aFXa level (aFXa ≥ 0.1 IU/mL), because low aFXa trough increases asymptomatic DVT risk ¹¹, 2) 90-day symptomatic VTE, and 3) 90-day clinically relevant bleeding. Symptomatic VTE was defined as any symptomatic deep vein thrombosis or pulmonary embolus with imaging confirmation. Screening duplex ultrasound was not performed, as suggested by current American College of Chest Physicians guidelines ². Clinically relevant bleeding was defined as any bleeding that changed the course of care ²¹; this included bleeding requiring enoxaparin cessation, unexpected transfusion, or procedural (interventional radiology or operating room) intervention. Chart review and mandatory phone calls at 90 days identified events that occurred at other facilities; when identified, records were obtained for confirmation.

Analysis plan

Study data were uploaded to a secure, online Research Electronic Data Capture platform.

Descriptive statistics compared patient level factors including individual VTE risk using the 2005 Caprini score ²² and surgical details, by group.

The proportion of patients who achieved the primary effectiveness and primary safety outcomes were compared, by group, using the chi-squared or Fishers exact test.

The survival analysis log-rank test compared 90-day VTE and 90-day bleeding, by group. No patient was lost to followup and the censoring rate of this survival analysis was zero.

Sample size calculation

Historical data showed that the two institutions admitted 14 eligible patients monthly. Similar studies showed that high proportions (~99%) of patients consented and 70% of these would produce primary outcome data ^{8,9,14}. We estimated that 116 patients (58 per group) could be consented within the planned 12 month study period.

We assumed 32.6% of thoracic surgery patients receiving enoxaparin 40mg once daily would have adequate anticoagulation (peak aFXa level ≥ 0.3 IU/mL) ⁸, and that 82% of patients would have adequate anticoagulation in response to once daily weight-tiered enoxaparin dosing, based on data from women having caesarean section ¹⁵. Using alpha of 0.05 and beta of 0.9, at least 23 patients per group would be required. Thus, anticipated recruitment exceeded the minimum number of required patients.

Based on existing trials data from thoracic surgery patients receiving enoxaparin 40mg once daily ⁸, low (~1%) rates of 90-day VTE and bleeding were anticipated. Thus, it was impossible to adequately power the study for a clinical endpoint.

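### The trough is sampled 12 hours after a once-daily dose, so the secondary outcome is a mid-interval level and can only equal or overstate the share at or above 0.1 IU/mL before the next dose

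*Combined protocol and SAP*

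**What the plan says.** The sampling times are given once, in Study Design: "We examined enoxaparin pharmacokinetics using steady state peak and trough aFXa levels, drawn at 4 and 12 hours after the third dose".

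Dosing is once daily in both cohorts. For Cohort 1, Study Design says "all patients received fixed dose enoxaparin prophylaxis at 40mg once daily". For the second cohort it says "Cohort 2 was revised to weight-tiered, daily enoxaparin", and the Sample size calculation section confirms this with "once daily weight-tiered enoxaparin dosing".

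Study Outcomes lists as the first secondary outcome "achievement of adequate trough aFXa level (aFXa ≥ 0.1 IU/mL), because low aFXa trough increases asymptomatic DVT risk". That definition does not repeat the sampling time. It also does not say at what time after dosing, or under what dosing interval, the 0.1 IU/mL cut-off was established. The document describes no sample at 24 hours or immediately before the next dose, and gives no reason for choosing 12 hours.

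**The concern.** A trough is the lowest level in a dosing interval, reached just before the next dose. With once-daily dosing the next dose is due at about 24 hours, so a 12-hour sample has roughly half the interval, and further decline, still ahead of it.

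The label matters because it carries a clinical rationale: the outcome is justified by a link between low trough and asymptomatic DVT. A reader told that a given share of patients had an adequate trough would take it that they stayed at or above 0.1 IU/mL until the next dose. The trial did not measure that. What is at stake is the absolute proportion reported in each cohort and the conclusion drawn from it.

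**Working it through.** **The plan's own figure.** The only design figure that can be recomputed is the 23 patients per group, for 32.6% against 82% on the peak outcome. I took alpha 0.05 two-sided and read the stated beta of 0.9 as power.

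- Uncorrected: n = [1.96·√(2 × 0.573 × 0.427) + 1.2816·√(0.326 × 0.674 + 0.82 × 0.18)]² / 0.494² = 18.9, so 19.
- With continuity correction: (18.9/4)·[1 + √(1 + 4/(18.9 × 0.494))]² = 22.8, so 23.

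The figure reproduces. It concerns the peak and plays no part in this point.

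**Step 1: position in the interval.** Sampling is at 12 h and the interval is 24 h (both from the plan). 12/24 = 50%, so the sample is at mid-interval.

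**Step 2: direction.** If no dose is given between 12 and 24 h and the level does not rise in that time, then C(24) ≤ C(12) for every patient. Everyone at or above 0.1 at 24 h is also at or above 0.1 at 12 h, so the 12-hour share is at least the pre-dose share. This needs no half-life. The plan's own labels (4 h as peak, 12 h as trough) already treat the level as falling.

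**Step 3: illustration of size.** The documents give no half-life. I assume first-order decline with half-life h from 4 to 8 hours:

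C(t) = C(4) × 2^(−(t−4)/h)

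The starting value is the plan's target range: "Goal peak aFXa (0.3-0.5 IU/mL) was chosen to maximize VTE risk reduction while minimizing bleeding".

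| Assumed h (hours) | C(12)/C(24) = 2^(12/h) | C(12) from peak 0.3–0.5 | C(24) from peak 0.3–0.5 | C(24) if C(12) = 0.10 | Peak needed for 0.1 at 24 h = 0.1 × 2^(20/h) |
|---|---|---|---|---|---|
| 4 | 8.0 | 0.075–0.125 | 0.009–0.016 | 0.013 | 3.2 |
| 5 | 5.3 | 0.099–0.165 | 0.019–0.031 | 0.019 | 1.6 |
| 6 | 4.0 | 0.119–0.198 | 0.030–0.050 | 0.025 | 1.0 |
| 7 | 3.3 | 0.136–0.226 | 0.041–0.069 | 0.030 | 0.72 |
| 8 | 2.8 | 0.150–0.250 | 0.053–0.088 | 0.035 | 0.57 |

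For a goal-range peak to be at 0.1 or more at 12 h, the half-life must be at least 8/log₂(5) = 3.4 h (peak 0.5) to 8/log₂(3) = 5.0 h (peak 0.3). At 24 h the requirement is 20/log₂(5) = 8.6 h to 20/log₂(3) = 12.6 h.

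**Step 4: whole cohorts, not only goal-range patients.** Assume log-normal 4-hour peaks with log-SD σ, centred so that the share at or above 0.3 equals the plan's 32.6% or 82%. The share at or above 0.1 at time t is then 1 − Φ((ln c − μ)/σ), where c is the 4-hour peak that decays to 0.1 by time t. Over assumed σ of 0.25 to 0.5 and h of 4 to 7 hours:

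| Share with peak ≥ 0.3 | Share ≥ 0.1 at 12 h | Share ≥ 0.1 at 24 h |
|---|---|---|
| 32.6% | 5.5% to 78.1% | 0.0% to 1.3% |
| 82% | 40.7% to 98.4% | 0.0% to 19.8% |

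At σ = 0.35 and h = 5 hours, for example, the pairs are 31.5% against 0.0%, and 81.2% against 0.01%.

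**The case against.** The strongest reply is that nothing is hidden. Study Design states the 12-hour time, which in so short a document serves as the working definition of trough. No section mentions 24 hours after a dose or claims adequacy over the whole interval, so as a measure of the 12-hour level nothing is overstated. If the source cited for the 0.1 cut-off used 12-hour samples, then threshold, timing and DVT rationale agree and only the word is wrong. The magnitudes rest wholly on an assumed half-life. The finding that no goal-range patient passes at 24 hours holds because the assumed range stops at 8 hours, short of the 8.6-hour crossover for a peak of 0.5. The dose-adjustment figure is not shown, so an intervening dose cannot be strictly excluded. Finally, a pre-dose sample judged at 0.1 would, on these same figures, hardly distinguish patients, so the 12-hour draw may be the more informative one.

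Much of this stands. The sizes are illustrative, the direction is conditional as stated, the source of the cut-off cannot be checked here, and there is no case for a different sampling time. What does not stand is that disclosing the time settles the matter. A 12-hour level is not the trough of a 24-hour interval even when its timing is stated, and the outcome definition uses the word, with a clinical rationale attached, without repeating the time. A match with the cited source would rescue the rationale but not the label.

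**Conclusion.** The concern holds. As written, the outcome would support a statement about trough levels that the sampling cannot provide; it supports a statement about hour 12 only.

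The direction is firm given two conditions: no dose between 12 and 24 hours, and no rise in level over that time (assay noise aside). The size is not known. Under assumed half-lives of 4 to 8 hours the 12-hour level is 8.0 to 2.8 times the 24-hour level, enough for the same patient to be adequate on one reading of trough and inadequate on the other.

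The effect is limited to the absolute proportions for one secondary outcome. Both cohorts are sampled at the same time, so no between-group bias is shown, and comparing 12-hour levels remains valid as such. The peak-based primary outcomes, the peak-targeted adjustment algorithm and the sample size are untouched.

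**What to change.** In Study Design and Study Outcomes, rename the outcome 12-hour aFXa ≥ 0.1 IU/mL. State that the pre-dose (24-hour) trough was not measured, and limit any conclusion to the 12-hour time point.

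A useful addition, though the point does not depend on it, is one sentence giving the sampling time and dosing interval behind the 0.1 IU/mL cut-off in the cited source. If they match a 12-hour sample, the asymptomatic-DVT rationale can stay. If not, say that the link is not established for this measurement.

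No change of sampling time is proposed, since accrual ended on March 25, 2019. The cost is the wording of one outcome and no new data. The trial gives up a full-interval trough claim that its sampling could not support.

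### The two sites are pooled in both primary tests of a before/after design, so any shift in site mix between cohorts would be counted as a dosing effect; a site-stratified comparison should be added

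*Combined protocol and SAP*

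**What the plan says.** The Study Design section describes a sequential comparison: "The study was designed prospectively as a pre/post trial to examine the impact of a change in practice". The fixed-dose period comes first: "Cohort 1 accrued between September 21, 2017 and May 8, 2018, and all patients received fixed dose enoxaparin prophylaxis". The weight-tiered period follows without overlap: "Cohort 2 accrued between August 9, 2018 and March 25, 2019". No randomisation, site quota, matching or stratification is described.

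There are two recruiting centres. The Sample size calculation gives their accrual only as a combined figure: "Historical data showed that the two institutions admitted 14 eligible patients monthly".

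For the primary outcomes (peak aFXa at or above 0.3 IU/mL for effectiveness, and avoiding 0.5 IU/mL or more for safety), the Analysis plan states: "The proportion of patients who achieved the primary effectiveness and primary safety outcomes were compared, by group, using the chi-squared or Fishers exact test". Neither test has a site term.

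The baseline comparison is descriptive: "Descriptive statistics compared patient level factors including individual VTE risk using the 2005 Caprini score", together with surgical details. Site is not named in that list, which is open-ended, and no adjustment follows from it.

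**The concern.** In a trial randomised within site, the allocation balances site between arms, so a pooled test is protected. Here calendar date sets the arm, and the text states nothing that takes the place of that balance. Recruitment also stopped and restarted under a revised regimen, so equal site shares in the two periods cannot be presumed.

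The outcome is a laboratory value on a timed draw, cut at fixed thresholds, and the text mentions no central laboratory. If assay, draw timing or case mix differ between sites, the proportion crossing a threshold can differ too.

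This source of bias is distinct from drift over time, because it arises even if each site is perfectly stable throughout. A change in who recruited could then create or hide a between-cohort difference, and the stated test could not reveal it.

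**Working it through.** **Inputs from the documents** (Sample size calculation): "We assumed 32.6% of thoracic surgery patients receiving enoxaparin 40mg once daily would have adequate anticoagulation"; 82% assumed under weight-tiered dosing; alpha 0.05; minimum 23 per group; planned 58 per group. I read the stated beta of 0.9 as 90% power and the test as two-sided. I treat 58 as evaluable patients, which is what the accrual figures give: 14 × 12 × 0.99 × 0.70 = 116.4, or 58 per group.

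**Assumed inputs.** Site shares by cohort and site-specific outcome rates are not in the text. I use share shifts of 10 to 30 points and site differences of 20 to 30 points.

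**1. The plan's own figure.** The mean of 0.326 and 0.82 is 0.573, and the difference is 0.494.
- Without continuity correction: n′ = [1.960 × √(2 × 0.573 × 0.427) + 1.282 × √(0.326 × 0.674 + 0.82 × 0.18)]² / 0.494² = 18.9, so 19.
- With continuity correction: n = (n′/4) × [1 + √(1 + 4/(n′ × 0.494))]² = 22.8, so 23.

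The stated 23 per group is reproduced, with the correction.

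**2. Bias formula.** Let w1 and w2 be one site's share in cohorts 1 and 2, pA and pB the two sites' rates on fixed dosing, and δ a dosing effect common to both sites.
- Cohort 1 rate: w1·pA + (1 − w1)·pB
- Cohort 2 rate: w2·pA + (1 − w2)·pB + δ
- Difference: δ + (w2 − w1)(pA − pB)

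The second term is zero if either the share shift or the site difference is zero.

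**3. False rejection with δ = 0, 58 per group, cohort 1 rate 32.6%.** The chi-squared and Fisher columns sum binomial probabilities over all outcome pairs with p at or below 0.05. The Cochran-Mantel-Haenszel (CMH) column is simulated, 100,000 runs per row, without continuity correction.

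| Share shift × site difference (points) | False difference | Uncorrected chi-squared | Fisher | Site-stratified CMH |
|---|---|---|---|---|
| 10 × 20 | 2 points | 5.5% | 3.6% | 5.1% |
| 20 × 20 | 4 points | 7.2% | 4.9% | 4.9% |
| 20 × 30 | 6 points | 10.1% | 7.1% | 4.9% |
| 30 × 30 | 9 points | 16.6% | 12.4% | 5.0% |

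Fisher looks better partly because it is conservative: by the same enumeration it rejects only 3.2% of the time when there is no bias at all. At 23 per group, the 30 × 30 case gives about 9.7% with chi-squared and 5.4% with Fisher.

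**4. Against the planned effect.** The planned effect is 82 − 32.6 = 49.4 points. Since √0.494 = 0.70, site mix alone would need about a 70-point share shift together with a 70-point site difference. The smallest significant difference at 58 per group is about 18 points.

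**5. A smaller effect.** With an assumed true effect of 25 points, simulated power of the pooled chi-squared depends on the direction of the shift. At 20 × 20 it is about 62% or 90%, against about 78% for CMH either way. At 30 × 30 it is roughly 40% or above 95%, against about 76% to 79%.

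**6. Price of stratifying when it was not needed.** With shares 0.5 ± d/2, the stratified comparison keeps a fraction 1 − d² of the information. At d = 0 nothing is lost. At d = 0.2 the fraction is 0.96, and power of about 78% falls to about 76%. At d = 0.3 it is 0.91, and power is about 74%.

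**The case against.** The strongest reply is that this is hypothetical. Bias needs both a share shift and a site difference, and the text shows neither. Where it describes the sites, it describes them as alike: the same epidural practice at both, and "Both sites encountered insurmountable issues with pharmacist dose rounding". Draw times are fixed by protocol. The two accrual windows are almost equal (229 and 228 days from the stated dates), and nothing suggests that a site dropped out. All of this stands. A reader might infer that site mix did shift, or that the rounding problem shows a contrast between pharmacies; the documents support neither. That sentence reports a shared experience.

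A reader might also infer that no site counts exist. That cannot be said: Figure 1, which covers enrolment and allocation, is not reproduced here. Even if it gives counts, the stated tests would not use them.

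The chi-squared inflation figures are not the whole picture. The plan equally allows Fisher, under which the 20 × 20 case stays at about 5%, and the 23 per group reproduces only with a continuity correction. This stands, so both columns must be reported.

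It is tempting to say that the safety outcome is especially exposed. No rate for it is given, so this cannot be shown. If, as an assumption, 5% overall reached 0.5 IU/mL with equal site shares, the sites could differ by at most 10 points. A 20-point shift would then give at most 2 points, and Fisher would reject about 2% of the time (4% against 6%, 58 per group).

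Finally, accrual ended in March 2019 and the document is dated June 2020. Replacing the primary test outright at that stage would itself be open to criticism. This argues for adding the stratified analysis and disclosing when it was added, but not for leaving site out.

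**Conclusion.** The concern holds as a conditional weakness with a cheap remedy. Two institutions, cohorts set by calendar period, no stated control of site mix and primary tests without a site term leave the pooled comparison unprotected. Whether it is biased in fact is unknown.

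For effectiveness, the assumed scenarios put the false difference at 4 to 9 points and the false-rejection rate at about 7% to 17% (uncorrected chi-squared) or 5% to 12% (Fisher). At 10 × 20 points the effect is negligible. These figures rest on 58 evaluable patients per group, a 32.6% base rate and assumed site shares and rates.

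A 49.4-point difference could not plausibly be produced by site mix. That margin gives less comfort than it seems to, because the 82% was taken from women having caesarean section, so a smaller true effect is possible and could be inflated or masked. For the safety outcome the size of the problem is undetermined.

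**What to change.** For both primary outcomes, add to the Analysis plan:
- a Cochran-Mantel-Haenszel test with site as stratum (exact version if counts are sparse);
- a Mantel-Haenszel risk difference with 95% confidence interval;
- a table of each outcome by site and cohort, with denominators.

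Base the between-cohort conclusion on the stratified estimate. Report the plan's pooled chi-squared or Fisher result beside it, and state that the stratified analysis was added after accrual.

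The cost is one extra table, a post-accrual change to disclose, and about 0 to 2 points of power for share shifts up to 20 points (about 4 at a 30-point shift if the sites turn out not to differ). It needs the site of each patient, which should be on record although the text does not say so. Stratifying by site does not remove calendar-time confounding, which belongs to the declared before/after design and should still be stated as a limitation.

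### Non-randomised pre/post comparison with only a crude 2x2 test for the primary outcomes: no analysis stratified or displayed by weight tier is stated, although weight sets the cohort 2 dose

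*Combined protocol and SAP*

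**What the plan says.** Study Design describes the comparison as follows: "The study was designed prospectively as a pre/post trial to examine the impact of a change in practice". The two periods do not overlap. On the first: "Cohort 1 accrued between September 21, 2017 and May 8, 2018, and all patients received fixed dose enoxaparin prophylaxis at 40mg once daily". On the second: "Cohort 2 accrued between August 9, 2018 and March 25, 2019". No randomisation, matching or stratification is described.

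In cohort 2 the starting dose depends on weight: "Patients <70kg received 30mg, patients 70kg to 89.9kg received 40mg", and those at 90 kg or more received 50 mg. Compared with cohort 1, the starting dose is therefore lower in the lightest tier, equal in the middle tier and higher in the heaviest.

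Study Outcomes names two primary outcomes: peak aFXa of at least 0.3 IU/mL for effectiveness, and for safety, "The primary safety outcome was avoidance of over-anticoagulation", with the threshold at 0.5 IU/mL. Under Analysis plan, the proportions for both "were compared, by group, using the chi-squared or Fishers exact test". Patient factors are compared descriptively by group. Caprini score and surgical details are named there and weight is not, although the list is open. No regression, stratified test or breakdown by weight tier is stated.

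**The concern.** There are two separate issues.

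The first is case mix. The tiered regimen presumes that weight affects the aFXa response to a given dose. If lighter patients reach 0.3 IU/mL more often on a given dose, and cohort 2 holds more of them, the crude proportion rises even when the regimen has no effect. A descriptive table may reveal such an imbalance but does not correct the test.

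The second is averaging, and it needs no imbalance. The pooled contrast answers the stated question about a change in practice and is a legitimate average effect. But it combines a dose reduction, no change and a dose increase, so opposite movements in the outer tiers can cancel.

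What is at stake is mainly how a modest effectiveness difference would be read. The planned 82% comes from women having caesarean section (Sample size calculation), so a smaller effect in thoracic patients cannot be excluded.

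**Working it through.** **The plan's own figure.** Inputs from Sample size calculation: p1 = 0.326, p2 = 0.82, alpha 0.05 (taken as two-sided), and the stated beta of 0.9 read as 90% power. The pooled-variance formula is n = [1.960·√(2·0.573·0.427) + 1.282·√(0.326·0.674 + 0.82·0.18)]² / 0.494² = 18.9. The continuity correction gives (18.9/4)·[1 + √(1 + 4/(18.9·0.494))]² = 22.8, so 23 per group, as stated. The sample size is not in question. The planned number is 14 × 12 × 0.99 × 0.70 = 116.4, or 58 per group; since the 70% is already applied, I take 58 as evaluable.

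**Assumptions not in the document.** Cohort 1 tier mix (<70 / 70-89.9 / ≥90 kg) is 30/40/30%. Adequacy by tier, identical in both cohorts (no dosing effect), is 60/30/10% (steep) or 50/30/20% (milder). Cohort 2 mix is unchanged, 40/40/20% or 50/40/10%.

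**Spurious difference.** The crude rate is Σ(mix × tier rate). Cohort 1, steep: 0.3·0.6 + 0.4·0.3 + 0.3·0.1 = 0.33. Cohort 2 at 50/40/10: 0.5·0.6 + 0.4·0.3 + 0.1·0.1 = 0.43. Rejection rates come from exact enumeration of two binomials with n = 58:

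| Tier rates | Cohort 2 mix | Crude rates | Spurious difference | Chi-squared | Fisher |
|---|---|---|---|---|---|
| either | 30/40/30 | 0.33 v 0.33 | 0 | 5.0% | 3.2% |
| milder | 40/40/20 | 0.33 v 0.36 | +3 | 6.2% | 4.2% |
| steep | 40/40/20 | 0.33 v 0.38 | +5 | 8.5% | 5.9% |
| milder | 50/40/10 | 0.33 v 0.39 | +6 | 10.0% | 7.1% |
| steep | 50/40/10 | 0.33 v 0.43 | +10 | 19.3% | 14.6% |

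**When this could decide the result.** From 19/58, the smallest significant rise is to 30/58 (19.0 points, chi-squared) or 31/58 (20.7 points, Fisher). A spurious 3 to 10 points is material there. For 32.6% v 82%, a rise of 49.4 points, power is above 99.9% and the conclusion would not change.

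**Safety.** No rate is given. At assumed tier rates from 10/3/1% (crude 4.5%) to 20/10/5% (crude 11.5%), the same shifts add 0.9 to 3 points; rejection is 5.0-7.8% (chi-squared) or 1.2-4.1% (Fisher).

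**Stratified estimate.** The Mantel-Haenszel risk difference is Σw(p2 − p1)/Σw over tiers, with w = n1·n2/(n1 + n2). In 200,000 simulations per effectiveness scenario it averages about 0 and its test rejects about 5% under every shift. Its 95% half-width, in points, against the crude one:

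- steep rates: 15.7 v 17.1 with equal mix, 17.2 v 17.5 at 50/40/10;
- milder rates at 50/40/10: 17.9 v 17.5;
- weight unrelated to adequacy (33% in all tiers) at 50/40/10: 18.0 v 17.1;
- safety at 50/40/10: 8.6 v 8.2 (10/3/1%) and 12.8 v 12.2 (20/10/5%).

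**Averaging with equal mix.** Let adequacy fall from 60% to 35% below 70 kg, stay at 30% in the middle, and rise from 10% to 25% at ≥90 kg. The cohort 2 rate is 0.3·0.35 + 0.4·0.3 + 0.3·0.25 = 0.30, against 0.33. Crude and Mantel-Haenszel both show −3 points and reject about 6.5%, so stratifying does not reveal the pattern; only a display by tier could.

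**Precision by tier.** At 17/23/17 patients per cohort (58 × 30/40/30%), the Wald half-width 1.96·√[(p1q1 + p2q2)/n] in this example is 32.5, 26.5 and 25.0 points. Chi-squared power within the outer tiers is 33% and 20%. For safety, 0/17 v 0/17 still leaves a score interval of ±18 points.

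**The case against.** The strongest reply is that the bias needs a systematic weight shift for which the document gives no evidence. The same two sites and the same eligibility criteria serve both cohorts, and chance imbalance is already covered by the test's error rate. The largest inflation needs the heaviest tier to fall from 30% to 10% of patients, and a comparison of tier mix at 58 per group would detect that about 78% of the time. The planned descriptive comparison might therefore flag it, if weight is included. The smaller 40/40/20 shift would be flagged only about 23% of the time, but it inflates error little. For safety, Fisher's test stays below 5% in every scenario tried. All of this stands, and it limits the importance of the point.

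Some stronger readings are tempting but unsupported:

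- **That the cohorts differ in weight.** No section says so.
- **That the interrupted 0.5 mg/kg phase distorted the comparison.** The plan reports: "Nine patients in the 0.5mg/kg group who received rounded doses were dropped". Those patients belong to neither compared cohort, so dropping them says nothing about the weight mix. The 93 days between cohort 1 closing and the tiered cohort opening show only that the cohorts are separated in time.
- **That a tier table would show who gained or lost.** Half-widths of 25 to 33 points do not allow this. Nor would a null result at 70-89.9 kg, where the starting dose is the same, be reassurance: power there is 11% for a 10-point shift and 29% for 20 points.

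**Conclusion.** The point holds in conditional form. The only stated primary comparison is crude, in a non-randomised design, and it ignores the variable that sets the cohort 2 dose. If the weight mix shifted as assumed, 3 to 10 points of an effectiveness difference would be case mix, with rejection of 6-19% (chi-squared) or 4-15% (Fisher) under no dosing effect. The tier rates and mixes behind these figures are assumptions; the document gives neither.

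A reader might infer that the crude test is invalid or that a positive result would be an artefact. The document supports neither. The pooled contrast is a valid average effect of the practice change when case mix is comparable, and an effect near the planned size would survive shifts of this order. Inflation for safety is small, so the gain there is mainly in reporting. Severity is minor to moderate, and the remedy is a cheap improvement.

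**What to change.** Keep the planned crude test. Beside it, for each primary outcome, report:

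1. a Mantel-Haenszel cohort risk difference with 95% CI, stratified by the three weight tiers;
2. a descriptive by-tier table of counts and risk differences with exact or score intervals, showing the share of each cohort in each tier.

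Label both as post hoc: the document is dated June 19, 2020, 452 days after accrual ended. State that the by-tier estimates are imprecise. Word the conclusion as an association with the practice change, because adjusting for weight cannot remove period effects.

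The cost is a small amount of analysis on weight data that should be in hand, since cohort 2 was dosed by weight. The stratified half-width runs from about 1.4 points narrower to about 1 point wider than the crude one, depending on how strongly weight predicts the outcome and how unequal the mix is. No new patients or data collection are needed.

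### Does the 82% response assumed for weight-tiered dosing undermine the sample size of 23 per group?

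*Combined protocol and SAP*

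**What the plan says.** Study Design describes cohort 1, in which "all patients received fixed dose enoxaparin prophylaxis at 40mg once daily". For cohort 2 it gives the revised tiers: "Patients <70kg received 30mg, patients 70kg to 89.9kg received 40mg", and those at 90kg or more received 50mg. Reference 15 is cited for this tiered regimen. Study Design also describes later dose changes: "All patients with identified out-of-range levels received dose adjustment and repeat aFXa levels per Figure 2".

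Under Study Outcomes, "The primary effectiveness outcome was adequate peak aFXa", with a threshold of 0.3 IU/mL. Under Analysis plan, the proportions reaching the primary outcomes "were compared, by group, using the chi-squared or Fishers exact test".

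The Sample size calculation begins with feasibility: "We estimated that 116 patients (58 per group) could be consented within the planned 12 month study period". It then assumes 32.6% adequacy on 40mg in thoracic patients, "and that 82% of patients would have adequate anticoagulation in response to once daily weight-tiered enoxaparin dosing", the latter "based on data from women having caesarean section" and again citing reference 15. With alpha 0.05 and a stated beta of 0.9 (evidently meaning 90% power), it arrives at a minimum of 23 per group and notes that expected recruitment is larger.

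**The concern.** The two planning rates come from different populations, and the tiers limit how far apart they can be in one population. Compared with cohort 1, patients under 70kg receive less, those from 70kg to 89.9kg receive the same, and only those at 90kg or more receive more. Nearly all of a rise from 32.6% to 82% would therefore have to come from the heaviest tier, which would need to hold about half the patients or more. The documents give no weight distribution; the only weight limit is the exclusion above 150kg.

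If the heavy share were well below half, 82% could not be reached and 23 per group would be too few. A non-significant comparison might then be read as coming from a study with 90% power when it had much less.

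**Working it through.** **Inputs.** From the Sample size calculation: p1 = 0.326, p2 = 0.82, alpha 0.05, power 0.90, 58 per group planned, 14 eligible patients a month for 12 months, 99% consent, 70% yielding outcome data. From Study Design: the tiers. Assumed, because not stated: a two-sided test.

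**1. The plan's own figure.** The mean rate is (0.326 + 0.82)/2 = 0.573 and the difference is d = 0.494.

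- Uncorrected: n = [1.96·√(2·0.573·0.427) + 1.2816·√(0.326·0.674 + 0.82·0.18)]² / 0.494² = (1.371 + 0.777)² / 0.2440 = 18.9.
- Continuity-corrected: n' = (n/4)·[1 + √(1 + 4/(n·d))]² = (18.9/4)·[1 + √(1 + 4/9.34)]² = 22.8, which rounds up to 23.

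The stated 23 reproduces. Exact power with Fisher's test at 23 per group is 0.908, against 0.885 at 22.

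**2. The bound from the tiers.** Let wH be the share at 90kg or more and c their adequacy on 40mg. Assume that (a) cohort 2 would have had 32.6% on 40mg, (b) adequacy does not fall as dose rises, and (c) the outcome is the first peak, before adjustment. The under-70kg tier then adds nothing or loses, the middle tier is unchanged, and

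p2 − p1 ≤ wH·(1 − c), so wH ≥ 0.494/(1 − c).

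- c = 0: 0.494/1 = 49.4%.
- c = 0.326: 0.494/0.674 = 73.3%.

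**3. What the planned size delivers.** 14 × 12 × 0.99 × 0.70 = 116.4. The 116 therefore seems to include the 70% already, although the text calls these patients consented, and 58 per group is probably the evaluable number. If 116 were consented before that loss, 116 × 0.70/2 = 40.6, or about 40 per group.

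Exact power by full enumeration of both binomials against 32.6%, with p ≤ 0.05 (uncorrected chi-squared / two-sided Fisher):

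| n per group | Power at 82% | Cohort 2 rate for 90% power | wH needed for that rate, c = 0 |
|---|---|---|---|
| 23 | 0.950 / 0.908 | 77.7% / 81.5% | 45.1% / 48.9% |
| 40 | 0.998 / 0.995 | 67.4% / 69.7% | 34.8% / 37.1% |
| 58 | >0.999 / >0.999 | 62.1% / 63.8% | 29.5% / 31.2% |

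Dividing the last column by (1 − c) covers less favourable cases. At 58 per group and c = 0.326, the share needed is 43.8% / 46.2%.

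**4. Range over the unknown share.** Best case (c = 0, everyone at 90kg or more adequate on 50mg, no loss under 70kg), with wH assumed:

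| wH | Power, 23 per group | Power, 58 per group |
|---|---|---|
| 20% | 0.29 / 0.19 | 0.59 / 0.51 |
| 30% | 0.56 / 0.43 | 0.91 / 0.87 |
| 40% | 0.81 / 0.71 | 0.99 / 0.99 |

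The rows of the second table are assumptions. Nothing in the documents says which one applies.

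**The case for a change.** The strongest case for a change is that naming a source does not show that the two rates can hold together. The tiers make this testable in principle, and the plan neither gives a weight mix nor varies the 82%. The larger enrolment lowers the heavy share needed to about 30% at best but does not remove the dependence on it. The closing remark that recruitment exceeds the minimum takes its comfort from the 23. A sentence on the detectable rate, a count by tier and a confidence interval would cost little.

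Much of this stands. The algebra is right under its three assumptions. The third is well supported, since levels are drawn after the third dose and the rationale for the outcome refers to the initial peak. Transfer from caesarean to thoracic patients is not argued.

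The step from there to a defect does not stand. The plan labels the rate an assumption, names the population, and takes it from the reference it cites for the tiered regimen, so it is a disclosed extrapolation. The first assumption is also demanding, because 32.6% comes from an external study whose weight mix would have to match cohort 2. Power always depends on the assumed effect, and the documents make no claim from a non-significant result. A tier count obtained after accrual cannot validate a planning input, and a confidence interval is good general reporting that does not depend on this point.

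**Conclusion.** No change is needed. The 23 per group is right for 32.6% against 82%, and it was a floor that the study did not rely on. The feasibility-based 58 per group, if evaluable, keeps 90% power down to a cohort 2 rate of about 62% (chi-squared) or 64% (Fisher), some 18 to 20 points below the assumed 82%. On the less likely reading of about 40 evaluable per group, the figure is about 67% to 70%. Much of any optimism in the 82% is therefore already absorbed.

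The limit of this conclusion is a heavy-tier share below about 30% in the best case, or below about 44% to 46% if adequacy on 40mg is also 32.6% in that tier. Power at 58 per group would then fall short of 90%, given the three assumptions set out in the working. The documents do not show that the share is that low, nor that it is not.

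Cohort 2 finished accruing in March 2019, and the document is dated June 2020. No enrolment decision remains, the planned chi-squared or Fisher comparison would be unchanged, and no stated power or size is shown to have been missed. A reader should simply take the 23 as conditional on its two inputs.
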